7.2.3 Assigning Attribution of AEs

The investigator **must** attempt to determine the cause of each event. To ensure consistency of AE/SAE causality assessments, investigators should apply the following guideline:

Related:

There is an association between the event and the administration of investigational study drug, a plausible mechanism for the event to be related to the investigational study drug and causes other than the investigational study drug have been ruled out, and/or the event re-appeared on re-exposure to the investigational study drug.

Possibly Related:

There is an association between the event and the administration of the investigational study drug and there is a plausible mechanism for the event to be related to investigational study drug, but there may also be alternative etiology, such as characteristics of the subject's clinical status or underlying disease.

Unlikely Related:

The event is unlikely to be related to the investigational study drug and likely to be related to factors other than investigational study drug.

Not Related:

The event is related to an etiology other than the investigational study drug (the alternative etiology must be documented in the study subject's medical record).

7.2.4 Classifying Action Taken With Study Drug

Classification	Definition
Dose Not Changed	Study Drug dose not changed in response to the AE
Drug Interrupted	Study drug administration interrupted in response to an AE
Drug Withdrawn	Study drug administration permanently discontinued in response to an AE
Not Applicable	Action taken regarding study drug administration does not apply. "Not applicable" should be used in circumstances such as when the investigational treatment had been completed before the AE began and no opportunity to decide whether to continue, interrupt or withdraw treatment is possible.

7.2.5 Classifying AE Outcome

Classification	Definition
Recovered/Resolved	Resolution of an AE with no residual signs or symptoms
Recovered/Resolved with sequelae	Resolution of an AE with residual signs or symptoms
Not Recovered/ Not resolved (continuing)	Either incomplete improvement or no improvement of an AE, such that it remains ongoing
Fatal	Outcome of an AE is death. "Fatal" should be used when death is at least possibly related to the adverse event.
Unknown	Outcome of an AE is not known (e.g., a subject lost to follow up)

7.2.6 Documenting and Reporting Serious Pretreatment Events and SAEs

All SAEs that occur after obtaining informed consent through the Follow-up visit, regardless of causality, must be reported by the investigator to the Sponsor designee for SAE reporting. See study manual for reporting specifics. In addition, all SAEs, including those that result in death, that occur after the Completion Visit and that are considered related to study drug(s) must be reported to Sponsor's designee within 24 hours.

SAEs will be recorded on the Clinical Trials SAE Form using a recognized medical term or diagnosis that accurately reflects the event. SAEs will be assessed by the investigator for severity, relationship to the investigational study drug(s) and possible etiologies. On the Clinical Trials SAE Form, relationship to study drug(s) will be assessed only as related or not related, and severity assessment will not be required. For the purposes of study analysis, if the event has not resolved at the end of the study reporting period, it will be documented as ongoing. For purposes of regulatory safety monitoring, the investigator is required to follow the event to resolution and report to Sponsor's designee the outcome of the event using the SAE Form.

The investigator is responsible for notifying the Sponsor within 24 hours of identifying an SAE, regardless of the presumed relationship to the investigational study drug. The SAE Form should be completed for new/initial events as well as to report follow-up information on previously reported events. Investigators are asked to report follow-up information as soon as it becomes available, to ensure timely reporting to Health Authorities.

The SAE Form should be faxed to Sponsor's designee using the fax cover sheet provided.

Alios BioPharma or its designees, as study Sponsor, is responsible for reporting suspected, unexpected, serious adverse reactions (SUSARs) involving the study drug(s) to all regulatory authorities, and participating investigators, in accordance with International Conference on Harmonisation (ICH) Guidelines, and/or local regulatory requirements, as applicable.

7.2.7 Documenting and Reporting of Pregnancy

Subjects will be counseled to inform the investigator of any pregnancy that occurs during study treatment and for 6 months after the last dose of study drug/s.

If a subject or the female partner of a male subject becomes pregnant while participating in the study, study treatment must be permanently discontinued immediately. The investigator must notify the Sponsor's Medical Monitor and CRO within 1 business day of the sites' knowledge of the subject's (or partner's) pregnancy, by utilizing the Pregnancy Initial Report Form. The subject or partner will be followed until end of pregnancy and the infant will be followed for 1 year after the birth, provided informed consent is obtained. A separate ICF will be provided to explain these follow-up activities. Pregnancy itself does not constitute an AE.

7.3 Follow-up of AEs and SAEs

Follow all AEs (serious and non-serious) until resolution or otherwise explained, the subject dies, the event stabilizes and is not expected to further resolve, or when alternative therapy is instituted, whichever occurs first. If alternative therapy is instituted, it should be documented.

Alios BioPharma may request that the investigator perform or arrange for supplemental measurements or evaluations to further clarify the nature of the event.

7.4 Sponsor's Review of AEs and SAEs

Alios BioPharma will maintain an ongoing review of all AEs and SAEs.

7.5 Special Safety Considerations

7.5.1 Creatine Kinase

Because nucleosides, as a class, have a known risk of mitochondrial toxicity, which is often manifest as muscle injury, this study will systematically assess study subjects for laboratory abnormalities which might be present after muscle injury.

Specifically, CK is checked throughout the study treatment period.

In the event a subject develops clinical signs suggestive of muscle injury (e.g., proximal weakness, myalgias), a thorough workup (e.g., assessment of CK, CK-MB fraction (or, alternatively, troponin), aldolase, myoglobin, calcium, phosphate, creatinine, and urinalysis) for muscle injury should be performed.

If a study subject's CK is found to be elevated $>3\times\text{ULN}$ (without a concomitant proportionate CK-MB or troponin elevation), the following stopping criteria for CK elevations should be applied ([Pasternak et al. 2002](#)):

In subjects (whether symptomatic or asymptomatic) without a clinical history to suggest etiology of CK elevation (e.g., recent exercise or exposure to medication with known risk of myopathy):

- If CK is $\geq 20\times\text{ULN}$, immediately re-draw and repeat the test. If the repeat remains $\geq 20\times\text{ULN}$, discontinue study medication
- If CK is $\geq 3 - < 20\times\text{ULN}$:
 - Continue study medication. Assess CK, CK-MB/troponin every ~72 hours (follow-up assessments) until the CK has normalized (follow-up assessments)
 - If any follow-up CK assessment is $\geq 20\times\text{ULN}$, discontinue study medication
 - if the 3rd follow-up CK assessment (i.e., ~9 days after CK elevation was first recognized) is \geq the prior follow-up CK assessment, discontinue study medication

In subjects with a clinical history suggestive of a non-study drug-related etiology for a CK elevation $\geq 3\times\text{ULN}$ (e.g., recent exercise or exposure to medication with known risk of myopathy):

- Study medication may be continued. These patients should immediately discontinue the putative cause of their CK elevation and the CK and CK-MB/troponin should be assessed every ~72 hours (=follow-up assessment).
- If initial CK is $\geq 3 - < 5\times\text{ULN}$, continue study medication unless follow-up CK

assessments are increased to $\geq 20 \times$ ULN

- If initial CK is $\geq 5 \times$ ULN, continue study drug dosing and assessing follow-up CK and CK-MB/troponin every ~ 72 hours. If the 3rd follow-up CK assessment (i.e., ~ 9 days after CK elevation was first recognized) is \geq the prior follow-up CK assessment, discontinue study medication.

For any study subject with a treatment-emergent CK > 1.5 - $< 3 \times$ ULN, consider repeat CK, CK-MB/troponin in ~ 72 hours and continue testing until CK decreases

If CK-MB/troponin rises commensurately with elevation of CK, an assessment for cardiac ischemic injury (e.g., serial EKG, troponin assessments) should be initiated.

If a subject that experiences CK elevations also demonstrates clinical or laboratory evidence of renal insufficiency/damage or other clinically significant muscle signs or symptoms (e.g., proximal weakness), study medication should be stopped regardless of the magnitude of the CK elevation.

In all cases where a CK $> 10 \times$ ULN or discontinuation of study drug is planned due to suspected muscle injury, the Sponsor Medical Monitor MUST be notified within 24 hours so that the clinical case and workup and treatment strategy can be discussed.

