4.6.1 Subject Treatment Discontinuation Criteria

If a subject's study drug treatment must be discontinued before the end of the treatment regimen, this will not result in automatic withdrawal of the subject from the study.

A subject's study drug treatment (AL-335, SMV and ODV) must be permanently discontinued if:

- The investigator believes that for safety reasons (e.g., AE), it is in the best interest of the subject to discontinue study drug treatment.
- The subject becomes pregnant.
- The subject has evidence of muscle injury (Section 7.5.1) or cardiac toxicity (Section 7.5.2 and 7.5.3).
- The subject has a Grade 4 rash; see Section 7.6.
- The subject has a Grade 3 or 4 allergic reaction; see Section 7.7.
- The subject has a confirmed Grade 4 ALT and/or AST value that is $>2\times$ the baseline value; see Section 7.9.
- The subject has a confirmed Grade 4 bilirubin value which is considered a sign of worsening liver disease, or for which there is no identifiable explanation; see Sections 7.8 and 7.9.
- The subject has severe worsening of hepatic disease.
- The subject has a confirmed diagnosis of pancreatitis.
- The subject has a Grade 4 AE or laboratory abnormality at least possibly related to 1 of the study drugs and which is considered clinically significant (laboratory abnormalities only).
- The subject requires treatment with any of the medications reported on the list of disallowed medications; see Section 5.12.
- The subject experiences inadequate virologic response or viral breakthrough (refer to Definitions)
- An event occurs which triggers the study treatment stopping criteria (Section 4.7.1)

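### Protocol 7.5.1 writes no 20×ULN follow-up CK stop for subjects with a suggested non-drug cause and an initial CK of 5×ULN or more

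*Protocol*

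**What the plan says.** Section 7.5.1 sets CK stopping rules for subjects above 3×ULN without a proportionate CK-MB or troponin rise.

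**No suggestive history.** An initial CK of 20×ULN or more is redrawn at once, and treatment stops if the value is confirmed. From 3 to below 20×ULN, follow-up is about every 72 hours. A level rule ("If any follow-up CK assessment is" 20×ULN or more) stops treatment, and so does a third follow-up at or above the previous one.

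**History suggesting a non-drug cause.** Treatment may continue, with follow-up about every 72 hours. "These patients should immediately discontinue the putative cause of their CK elevation". Two bands follow:
- Initial CK 3 to below 5×ULN: "continue study medication unless follow-up CK" reaches 20×ULN or more. There is no trend rule.
- Initial CK 5×ULN or more, with no upper bound: "continue study drug dosing and assessing follow-up CK and CK-MB/troponin every" 72 hours or so. Treatment stops if the third follow-up is at or above the previous one. No CK level is given.

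**Rules for everyone.** Section 7.5.1 stops treatment for "clinical or laboratory evidence of renal insufficiency/damage" or clinically significant muscle signs, whatever the CK. Above 10×ULN, "the Sponsor Medical Monitor MUST be notified within 24 hours" so that the case and treatment strategy can be discussed. Section 4.6.1 requires discontinuation for evidence of muscle injury, citing 7.5.1. It also requires it when "The subject has a Grade 4 AE or laboratory abnormality at least possibly related to 1 of the study drugs" and, for laboratory abnormalities, the finding is considered clinically significant. Appendix F grades CK of 20×ULN or more as Grade 4.

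**The concern.** CK is the laboratory marker that 7.5.1 uses to look for muscle injury from nucleoside mitochondrial toxicity. Among bands starting at 3×ULN or above, the suggested-cause band from 5×ULN upwards is the only one without a 20×ULN stop, and 7.5.1 gives no reason. Two subjects with the same suggested cause and the same Grade 4 follow-up can be handled differently, and the one who started higher has no level-based stop. A site cannot tell whether this is intended.

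The branch can be reached in this trial. One of its examples of an alternative cause is a drug with known myopathy risk. Table 5-1 permits six statins with caution, and section 1.4 says simeprevir may raise statin concentrations. Exclusion criterion 14 bars CK above 1.5×ULN at screening, so 5×ULN on treatment is a clear rise from entry.

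**Working it through.** The plan states no figure to reproduce. The check applies the written rules to example CK paths. All values are multiples of ULN and are illustrative, not probabilities.

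| Branch, initial CK | Follow-ups 1 / 2 / 3 | 7.5.1 as written | With the proposed change |
|---|---|---|---|
| Suggested cause, 4 | 25 | Stop at ~72 h (25 ≥ 20) | Same |
| No history, 6 | 25 | Stop at ~72 h (25 ≥ 20) | Same |
| Suggested cause, 6 | 25 / 40 / 30 | No CK-based stop (no level rule; 30 < 40) | Stop at ~72 h |
| Suggested cause, 6 | 25 / 25 / 25 | Stop at ~9 days (25 ≥ 25) | Stop at ~72 h |
| Suggested cause, 6 | 18 / 9 / 4 | Continue | Continue |
| Suggested cause, 6 | 10 / 12 / 15 | Stop at ~9 days (15 ≥ 12) | Same |
| Suggested cause, 4 | 10 / 12 / 15 | Continue (never ≥ 20; no trend rule) | Same |
| Suggested cause, 22 | 30 / 45 / 44 | No CK-based stop (44 < 45) | Sponsor to specify |
| Suggested cause, 60 | 21 (first draw) | No stop at ~72 h | Sponsor to specify |

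**Timing.** The third follow-up falls at 3 × 72 h = 216 h = 9 days. Table 2-1 gives 8 or 12 weeks for Cohorts 6 to 12, which are open or planned. The earliest band-specific stop therefore comes after 9/56 = 16.1% of an 8-week course or 9/84 = 10.7% of a 12-week course. With a follow-up ceiling it could come at 3/56 = 5.4% or 3/84 = 3.6%.

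**Do the other rules supply the ceiling?**
- The Grade 4 rule in 4.6.1 reaches CK of 20×ULN or more, but it needs judgements of relatedness and clinical significance. Section 7.2.3 lets an event be possibly related when the association and mechanism fit "but there may also be alternative etiology". That allows the judgement without requiring it.
- The muscle-injury bullet in 4.6.1 carries no relatedness condition, but it refers back to 7.5.1, where this band has no level.
- The renal and muscle-sign stop does not depend on CK level, so it misses an isolated CK rise.
- The rule above 10×ULN requires a discussion, not a stop.

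**The case against.** The strongest reply is that the two bands use different kinds of rule on purpose: a level for low starters and a trend for high starters. A trend rule makes sense in a band with no upper bound, because the initial value may already exceed 20×ULN. The asymmetry also runs the other way: follow-ups of 10, 12 and 15×ULN stop a 6×ULN starter and not a 4×ULN starter. Every subject in the gap has passed 10×ULN, so the Medical Monitor must already be discussing treatment. An investigator could read a CK that climbs after the putative cause is removed as evidence of muscle injury under 4.6.1, or could decide that the history no longer explains it and apply the no-history rules. Section 7.5.1 also cites a clinical advisory that is not available here, so whether the banding follows it cannot be judged.

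Much of this stands. It limits the size of the point and rules out the simple claim that the higher band is weaker in every respect. It does not supply the missing stop: each route depends on a judgement, and the text neither requires nor forbids a change of branch. A different rule type does not explain 25/40/30×ULN from a 6×ULN start, since that subject began well below 20×ULN.

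**Conclusion.** The gap is real and minor. In the suggested-cause branch, an initial CK of 5×ULN or more carries no automatic stop on CK level. A rise to 25/40/30×ULN from 6×ULN meets no CK-based stop in 7.5.1, although the same first follow-up stops a 4×ULN starter.

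The gap needs all of the following: a suggested alternative cause, with the subject kept in that branch; an initial CK of 5×ULN or more; a follow-up of 20×ULN or more; no renal or muscle findings; and a CK judged unrelated or not clinically significant. This is probably uncommon. With 123 subjects dosed, section 1.2.1.2 reports no laboratory findings suggestive of a safety concern. No statistical figure changes.

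A reader might infer three stronger things that the documents do not support:
- That these subjects have no stopping rule. They have the trend stop and the other rules above.
- That any continuation after 20×ULN shows a failure. Follow-ups of 21/15/10×ULN are a falling CK, the kind of recovery this branch may be meant to allow.
- That the ceiling should cover every initial value in the band. A fall from 60 to 21×ULN is clear improvement, yet a flat ceiling would stop treatment. Staying below 20×ULN at about 72 hours needs a fall of more than 1 − 20/40 = 50% from 40×ULN and 1 − 20/60 = 67% from 60×ULN.

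**What to change.** In the suggested-cause branch of 7.5.1, for initial CK from 5 to below 20×ULN, add: *Discontinue study medication if any follow-up CK assessment is ≥20×ULN.* Keep the third-follow-up trend stop and leave the 3 to below 5×ULN band as it is.

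For initial CK of 20×ULN or more, the sponsor should choose and state a rule. One option is to stop if the first follow-up is 20×ULN or more and not lower than the initial value. That would stop the 22-to-30×ULN path at about 72 hours (30 ≥ 20 and 30 ≥ 22) and let the 60-to-21×ULN path continue (21 < 60). If the sponsor intends no ceiling from 5×ULN upwards, the protocol should say so and give the reason.

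The cost is one added sentence, plus a second if a rule for very high starters is written. No extra draws are needed, since follow-up about every 72 hours is already required. The downside is that a few subjects with a true non-drug cause may stop a short antiviral course early, with some risk of treatment failure. Section 1.2.1.2 describes extending treatment in Cohort 4 to limit relapse, so that risk matters here.

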7.5.2 Cardiotoxicity

A theoretical risk of nucleosides is mitochondrial toxicity that can manifest as cardiac toxicity/congestive heart failure. Surveillance for this theoretical risk will be done in this study via assessments of AEs, ECGs and echocardiograms, which will be obtained at specified timepoints during the treatment period in this study.

In order to effectively monitor for potential treatment-related cardiotoxicity during the study, subjects presenting at screening must have:

- ECG PR interval must be < 200 msec and there must be no evidence of any conduction blocks.
- echocardiogram ejection fraction (EF) must be $\geq 55\%$.

During the treatment period, emergence of or changes in symptoms or clinically significant findings in ECG may trigger the following stopping criteria:

If a first degree AV block is diagnosed and:

- The PR interval is > 200 msec but ≤ 240 msec, study drugs can be continued. Close monitoring with weekly ECG is recommended.
- The PR interval is > 240 msec but ≤ 300 msec (confirmed by a repeat triplicate analysis at least 30 minutes after the initial assessment), an assessment of the subject's clinical status, including symptoms, physical examination and other clinical parameters should be made. Based on this assessment, the study drugs may or may not be continued. Close monitoring with weekly ECG is recommended.

- The PR interval is >300 msec (confirmed by a repeat triplicate analysis at least 30 minutes after the initial assessment, irrespective of presence or absence of clinical symptoms), ODV must be discontinued. The Investigator and Sponsor Medical Monitor must determine whether or not continued dosing with AL-335 and SMV is acceptable for subjects that discontinue ODV.
- If a second degree or higher AV block is diagnosed (confirmed by a repeat triplicate analysis at least 30 minutes after the initial assessment and irrespective of presence or absence of clinical symptoms), ODV must be discontinued. The Investigator and Sponsor Medical Monitor must determine whether or not continued dosing with AL-335 and SMV is acceptable for subjects that discontinue ODV.

All study medications must be discontinued:

- In asymptomatic patients with no clinical evidence of congestive heart failure:
 - If the absolute decline from baseline in EF is >10% AND the post-baseline EF is <50%; e.g., 60% →49%)

NOTE: For asymptomatic subjects without clinical evidence of heart failure, but with an apparent decline in EF of >10%, an urgent repeat echocardiogram may be performed to confirm the finding. If confirmed and <50%, all study drugs should be discontinued as described above. If the confirmatory EF is ≤10%, the Investigator and Medical Monitor should perform a cardiology assessment (see below) and, based on the subject's overall clinical picture, decide whether or not to discontinue study drug.

- If the absolute decline from baseline in EF is >5% and ≤10%, an urgent unscheduled visit must occur for the assessment of the subject's clinical status, including symptoms, physical exam, and other clinical parameters. This assessment should occur before deciding whether to stop or continue study drugs.
- In symptomatic subjects (e.g., dyspnea, orthopnea) or subjects with signs of congestive heart failure (e.g., S3 gallop, pedal edema, pulmonary edema):
 - If the absolute decline from baseline in EF is ≥5% (e.g., 61%→54%)
 - The Investigator and Sponsor Medical Monitor may also deem it necessary to discontinue study drug in symptomatic subjects with an absolute decline from baseline in EF of <5%
- In asymptomatic or symptomatic subjects with clinical evidence of heart failure:
 - If absolute decrease in EF from screening is >10%, these subjects must undergo mandatory assessment (see below) and have an urgent cardiology referral; the EF decrease must be reported to the Medical Monitor within 24 hours so that the clinical case and workup and treatment strategy can be discussed.

Subjects with an absolute decrease from screening of $>5\%$ to $\leq 10\%$ in LVEF must have an urgent unscheduled visit for further assessment as soon as possible.

The cardiology assessment should include, but is not limited to, the following:

- Cardiopulmonary review of systems and physical examination,
- Troponin I assessment - (serial assessments may be indicated)
- BNP or Pro-BNP (serial assessments may be indicated)
- 12-lead ECG and
- Additional echocardiography (at study approved facility) – if clinically indicated, at a frequency determined by the Investigator’s judgment.

Echocardiography must be performed at study approved facility on any subject who develops symptoms or signs of possible congestive heart failure (e.g., dyspnea, orthopnea, S3 gallop, pedal edema) during the study, regardless of the timing of such symptoms, including during the Follow-up Period.

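### Protocol 7.5.2: the NOTE's cardiology-assessment trigger cannot operate as printed, and the action for an asymptomatic EF fall of more than 10 points with EF still at least 50% turns on that correction and on an ambiguous bullet heading

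*Protocol*

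**What the plan says.** Screening EF must be at least 55% (Protocol 4.3, criterion 4; repeated in 7.5.2). For a subject with no symptoms and no clinical evidence of heart failure, 7.5.2 then gives three instructions:

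- **Stop all drugs:** "If the absolute decline from baseline in EF is >10% AND the post-baseline EF is <50" per cent.
- **NOTE on an apparent fall of more than 10%:** "an urgent repeat echocardiogram may be performed to confirm the finding". If the fall is confirmed and EF is below 50%, drugs stop. Then: "If the confirmatory EF is ≤10%, the Investigator and Medical Monitor should perform a cardiology assessment", after which they decide on the overall clinical picture whether to stop.
- **Fall above 5% and up to 10%:** "an urgent unscheduled visit must occur for the assessment of the" subject's clinical status.

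Two further bullets follow. The first, "In symptomatic subjects (e.g., dyspnea, orthopnea) or subjects with signs of congestive heart failure", stops all drugs at a decline of 5% or more. The second is headed "In asymptomatic or symptomatic subjects with clinical evidence of heart failure". For a decrease from screening above 10% it says "these subjects must undergo mandatory assessment (see below) and have an urgent cardiology referral", with a report to the Medical Monitor within 24 hours. The next sentence carries no symptom or heart-failure qualifier: subjects whose LVEF has decreased from screening by more than 5% and up to 10% "must have an urgent unscheduled visit for further assessment as soon as possible".

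**The concern.** The NOTE's last branch states its threshold as an EF value where only a different value, or a decline, makes sense. A site cannot apply it as written and has to guess the correction. The guess changes what happens to a subject whose EF has fallen by more than 10 points but remains at 50% or above. The heading of the later bullet, which might settle the matter, can be read two ways.

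The heart is a stated target organ of odalasvir toxicity (1.3), safety is the primary endpoint (3.2.1), and up to 50 sites are allowed (Synopsis). At stake is consistent individual management: one site might do no more than an optional repeat echocardiogram where another arranges a cardiology assessment, an urgent referral and a 24-hour report for the same result.

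**Working it through.** Write B for baseline EF and p for the later EF, in whole percentage points.

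**1. The protocol's own examples.** 60 to 49: decline 60 − 49 = 11 > 10, and 49 < 50, so the asymptomatic stop is met as stated. 61 to 54: decline 61 − 54 = 7 ≥ 5, so the symptomatic stop is met as stated. Both core stops work.

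**2. The trigger as printed.** With B ≥ 55 and p ≤ 10, B − p ≥ 55 − 10 = 45 > 10, and p < 50. The mandatory stop is always met, so the stop-or-continue choice reaches no one.

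**3. Two candidate corrections.** (A) confirmatory EF ≥ 50%, the complement of the preceding sentence's below-50% condition. (B) confirmatory EF decline ≤ 10%, the complement of the NOTE's opening condition. For B = 65:

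| Repeat EF | Decline | NOTE under A | NOTE under B | Other rule for this subject |
|---|---|---|---|---|
| 49 | 16 | stop | stop | core stop |
| 53 | 12 | assess, then decide | no step | only the later bullet, if it applies |
| 57 | 8 | assess, unless limited to confirmed falls | assess | urgent visit required |
| 63 | 2 | assess, unless limited to confirmed falls | assess | none |

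B alone sends a refuted fall (65 to 63) to cardiology assessment and gives a confirmed 12-point fall no step in the NOTE.

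**4. The later bullet's heading.** Reading 1: the heart-failure qualifier limits both groups, so the asymptomatic subject above is outside the bullet. Reading 2: it limits only the symptomatic group, so that subject is inside it. For a fall of more than 10 points with EF ≥ 50%:

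| | Reading 1 | Reading 2 |
|---|---|---|
| Correction A | assessment and decision, but only if the optional repeat is done | mandatory assessment, referral, 24-hour report |
| Correction B | optional repeat only | mandatory assessment, referral, 24-hour report |

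The study-level rule in 4.7.1 also needs EF below 50%. Section 4.6.1 refers cardiac toxicity back to 7.5.2 and otherwise rests on investigator judgement.

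**5. Who can be in this zone.** B − p > 10 with p ≥ 50 requires B > 60. Whole-number p runs from 50 to B − 11, which is B − 60 values: none at B = 55 to 60; 1 at 61 (EF 50); 5 at 65 (EF 50–54); 10 at 70 (EF 50–59). The documents give no baseline EF distribution, so the share of subjects cannot be computed.

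**6. What monitoring remains.** In an 8- or 12-week regimen a subject in this zone at Week 4 has the next scheduled echocardiogram at Week 8 (Table 6-1). Between them come three ECG visits with symptom-directed examination (Weeks 5, 6, 7) and one chemistry panel (Week 6). Appendix B lists BNP or NT-pro-BNP among the chemistries but no troponin. The mandatory step would therefore mainly add troponin I and the referral.

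**The case against.** The strongest reply is that the larger fall is already handled. The later bullet names asymptomatic subjects. The sentence after it sets an unqualified urgent visit for falls above 5% and up to 10%. Both are measured from screening, so they read as paired tiers. Under Reading 1 a larger fall could require less than a smaller one, and the bullet would address mainly subjects already required to stop at 5 points. Neither is a plausible intent. This stands: context favours Reading 2. What remains is wording that does not say so plainly.

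A reader might infer three stronger things that the documents do not support:

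- **That 7.5.2 has a demonstrated hole.** The optional repeat is the only step where Reading 1 holds and either correction B applies or no repeat is done. The text does not establish that combination.
- **That a decline was evidently meant.** Correction A fits the sentence's subject, an EF value, and the sentence before it at least as well.
- **That the dog EF finding shows this pattern.** Section 1.3.1 describes a minor reduction of unstated size in the 26-week study, within the normal range and with cardiac index unaffected. The zone here needs a fall of more than 10 points. In humans, 1.2.1.2 reports no clinically significant echocardiogram findings suggesting a safety concern, apart from one PR-prolongation case.

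Divergence between sites is also limited. Centrally read echocardiograms should guide work-up decisions (6.2.6), the NOTE involves the Medical Monitor, and investigators must stop treatment when safety requires it (4.6.1). These points limit the severity. They do not make the printed trigger workable.

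**Conclusion.** The trigger is wrong as printed. That follows from the entry criterion and the stop rule alone, and it is certain. Which correction was intended is not settled. The action for an asymptomatic subject with a confirmed fall above 10 points and EF of at least 50% depends on that correction and on how the later heading is read; context suggests the bullet was meant to cover this subject.

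This is a minor-to-moderate correction to safety wording. It concerns only subjects with baseline EF above 60%, at an unknown frequency. The asymptomatic and symptomatic stops work as written. The EF decline tables in SAP 8.3.3 use their own cut-offs and are unaffected, so no analysis is lost. The zone widths assume EF read in whole points and declines taken as absolute points, as the protocol's examples imply.

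**What to change.** (a) The sponsor confirms the intended threshold, checking the signed protocol first in case a symbol was altered in the public copy, and corrects the NOTE. The corrected NOTE should say that a confirmed decline of more than 10 points with EF at 50% or above leads to the cardiology assessment and then a stop-or-continue decision. A repeat showing a decline above 5 and up to 10 points should follow the existing urgent-visit rule. Changing the trigger only to a decline of at most 10% would not be enough.

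(b) Reword the later heading to *In any subject, with or without symptoms or clinical evidence of heart failure*. State that the existing assessment, urgent referral and 24-hour report apply to every decrease above 10 points that is confirmed or not repeated. The repeat echocardiogram stays optional.

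The cost is two wording edits in 7.5.2 and a memo to sites. No cut-point, scheduled assessment or SAP text changes. The small downside is a few more cardiology assessments and referrals, using the assessment that 7.5.2 already defines.
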